## 6.6 Dose Modifications

**Note: Three toxicities have been identified as potentially overlapping with both BGB324 and pembrolizumab – diarrhea, rash and renal toxicity. Please see [Section 6.6.4](#) for the management of these toxicities.**

Other toxicities can be managed as described in [Section 6.6.1](#), [Section 6.6.2](#) and [Section 6.6.3](#).

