**Table 12: Dose Modification for BGB324-related Toxicity**

Grade (CTCAE)		Recommended Dose Modification
Grade 1 and Grade 2 (tolerable)		
Any occurrence		Maintain dose of 200 mg if toxicity is tolerated by the patient
Grade 2 (intolerable)		
1 st or 2 nd occurrence of same adverse event		Interrupt treatment until toxicity returns to baseline, Grade 1 or tolerable Grade 2 Resume dosing at 200 mg
3 rd occurrence of same adverse event		Interrupt treatment until toxicity returns to baseline, Grade 1 or tolerable Grade 2 Dose reduce to 100 mg
4th occurrence of same adverse event		Discontinue permanently
Grade 3		
1 st occurrence		Interrupt treatment until toxicity returns to baseline, Grade 1 or tolerable Grade 2 Dose reduce to 100 mg or Discontinue permanently if dose has already been reduced
2 nd occurrence of same adverse event at G3		Discontinue permanently
Grade 4		
1 st occurrence		Discontinue permanently
Notes:		

 
Treatment interruption for BGB324-related toxicity should be limited to 14 days
 
Dose reduction below 100 mg daily is not possible (a single capsule contains 100 mg BGB324)
 
Patients being considered for dose reduction or permanent discontinuation of BGB324, may be discussed with
 
		

Grade (CTCAE)	Recommended Dose Modification
the Medical Monitor	
• Patients require an ECG twice weekly for the first 2 weeks after recommencing BGB324 following an interruption (see Section 5.3.9 )	

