**Table 13: Dose modification of BGB324 for QTc Prolongation**

QTcF	Recommended BGB324 Dose Modification
Grade 1 (450-480 ms)	
Any occurrence	No dose modification required
Grade 2 (481-500 ms) - on two consecutive occasions per protocol assessments or investigator's judgement	
1 st occurrence	Interrupt treatment with BGB324: i) if QTcF reduces to $\leq$ Grade 1 by 14 days from initial recording, restart BGB324 at a reduced dose of 100mg or discontinue if no further dose reduction is possible. ii) if QTcF does not reduce to $\leq$ Grade 1 by 14 days from initial recording, discontinue BGB324 permanently.
$\geq$ 2 nd occurrence (following a previous dose reduction for QTcF)	Discontinue BGB324 permanently.
$\geq$ Grade 3 ( $\geq$ 501 ms)	
1 st occurrence	Interrupt treatment with BGB324: - if QTcF reduces to $\leq$ Grade 1 by 14 days from initial recording, restart BGB324 at a reduced dose of 100mg or discontinue treatment if dose reduction is not possible - if QTcF does not reduce to $\leq$ Grade 1, discontinue BGB324 permanently.
2 nd occurrence	Discontinue BGB324 permanently
Ventricular arrhythmia	
1 st occurrence	Discontinue BGB324 permanently
Notes:	
• Serum calcium, magnesium and potassium should be measured regularly whilst receiving BGB324; all abnormal results should be corrected	
• The mean QTcF value from triplicate ECG readings should be used when considering dose modification	

QTcF	Recommended BGB324 Dose Modification
	

• Treatment interruption for BGB324-related toxicity should be limited to 14 days

• Dose reduction below 100 mg daily is not possible (a single capsule contains 100 mg BGB324)

• Patients being considered for dose reduction or permanent discontinuation of BGB324 may be discussed with the Medical Monitor

• Patients require an ECG twice weekly for the first 2 weeks after recommencing BGB324 following an interruption (see Section 5.3.9)

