**Table 15: Pembrolizumab and BGB324 Dose Modification for Diarrhea**

Diarrhea with onset in the 2 nd cycle or later cycle	Pembrolizumab	BGB324
Grade 2-3	Withhold for up to 12 weeks of last dose 
 
• If resolved to Grade 0 or 1, restart pembrolizumab
 
• Permanently discontinue if not resolved to grade 0 or 1, or, there is an inability to reduce corticosteroid to <math>\leq 10</math> mg (prednisone or equivalent) per day
 
	Withhold for up to 14 days 
 
• If resolved to grade 0 or 1, restart BGB324 at 100 mg qd
 
• Permanently discontinue if not resolved to grade 0 or 1
 

Grade 4	Permanently discontinue	Permanently discontinue

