#### 6.6.4.2 Dose modifications for rash (including dermatitis, pruritus) – [Table 16](#)

**Table 16: Pembrolizumab and BGB324 Dose Modification for Rash**

Rash – onset during any cycle	Pembrolizumab	BGB324
Grade 2	Pembrolizumab can continue as scheduled	BGB324 can continue as scheduled
Grade 3 or severe	Withhold for up to 12 weeks of last dose 
 
• If resolved to grade 0 or 1, restart pembrolizumab
 
• Permanently discontinue if not resolved to grade 0 or 1, or, there is an inability to reduce corticosteroid to <math>\leq 10</math> mg (prednisone or equivalent) per day
 
	Withhold for up to 14 days. 
 
• If resolved to grade 0, 1 or tolerable grade 2, restart at 100 mg qd
 
• Permanently discontinue if not resolved to grade 0, 1 or tolerable grade 2
 

Grade 4	Permanently discontinue	Permanently discontinue

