## 6.8 Permitted and Restricted Concomitant Medications

In general, medications or vaccinations specifically prohibited in the exclusion criteria are not allowed during the ongoing trial. Treatment with antacids, proton pump inhibitors and histamine receptor 2 inhibitors can be initiated as rescue therapy after patients have been receiving BGB324 for one week, provided they are taken in the evening.

If there is a clinical indication for any medication or vaccination specifically prohibited during the trial, discontinuation from trial therapy or vaccination may be required. The investigator should discuss any questions regarding this with the Sponsor Clinical Director. The final decision on any supportive therapy or vaccination rests with the investigator and/or the patient's primary physician. However, the decision to continue the patient on trial therapy or vaccination schedule (see [Section 6.10](#)) requires the mutual agreement of the investigator, the Sponsor and the patient.

Patients should not receive BGB324 during periods of systemic corticosteroid treatment. If a patient requires treatment with systemic corticosteroids, BGB324 should be interrupted immediately. Treatment with BGB324 may be restarted upon completion of systemic corticosteroid therapy. BGB324 may be continued at the appropriate dosage during periods of topical and inhaled corticosteroid therapy.

Hormonal contraception for female breast cancer patients is contraindicated.

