## 6.11 Supportive Care Guidelines for Pembrolizumab

Patients should receive appropriate supportive care measures as deemed necessary by the treating investigator. Suggested supportive care measures for the management of AEs with potential immunologic etiology are outlined below. Where appropriate, these guidelines include the use of oral or intravenous treatment with corticosteroids as well as additional anti-inflammatory agents if symptoms do not improve with administration of corticosteroids. Patients receiving oral or intravenous corticosteroids must interrupt treatment with BGB324 throughout the duration of therapy.

Note that several courses of steroid tapering may be necessary as symptoms may worsen when the steroid dose is decreased. For each disorder, attempts should be made to rule out other causes such as metastatic disease or bacterial or viral infection, which might require additional supportive care. The treatment guidelines are intended to be applied when the investigator determines the events to be related to pembrolizumab.

Note: If after the evaluation the event is determined not to be related, the investigator does not need to follow the treatment guidance (as outlined below). Refer to [Section 6.6](#) for dose modification.

It may be necessary to perform conditional procedures such as bronchoscopy, endoscopy, or skin photography as part of evaluation of the event.

- **Pneumonitis:**

- For **Grade 2 events**, treat with systemic corticosteroids. When symptoms improve to Grade 1 or less, steroid taper should be started and continued over no less than 4 weeks.
- For **Grade 3-4 events**, immediately treat with i.v. steroids. Administer additional anti-inflammatory measures, as needed.
- Add prophylactic antibiotics for opportunistic infections in the case of prolonged steroid administration.
- **Diarrhea/Colitis:**  
Patients should be carefully monitored for signs and symptoms of enterocolitis (such as diarrhea, abdominal pain, blood or mucus in stool, with or without fever) and of bowel perforation (such as peritoneal signs and ileus).
  - All patients who experience diarrhea/colitis should be advised to drink liberal quantities of clear fluids. If sufficient oral fluid intake is not feasible, fluid and electrolytes should be substituted via i.v. infusion. For Grade 2 or higher diarrhea, consider GI consultation and endoscopy to confirm or rule out colitis.
  - For **Grade 2 diarrhea/colitis** administer oral corticosteroids.

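### Tables 15–17 restart BGB324 at 100 mg after Grade 3 diarrhea, rash or renal toxicity with no stop for recurrence or prior reduction, and the protocol does not say whether Table 12's stops still apply

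*Protocol*

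**What the plan says.** Section 6.6 names diarrhea, rash and renal toxicity as potentially overlapping between the two drugs and sends the reader to Section 6.6.4 for them. It continues: "Other toxicities can be managed as described in" Sections 6.6.1 to 6.6.3.

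Section 6.6.4 gives these BGB324 instructions at Grade 3:

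- Table 15 (diarrhea, onset in cycle 2 or later; one row for Grades 2–3): hold for up to 14 days, then "If resolved to grade 0 or 1, restart BGB324 at 100 mg qd".
- Table 16 (rash, Grade 3 or severe): hold for up to 14 days, then "If resolved to grade 0, 1 or tolerable grade 2, restart at 100 mg qd".
- Table 17 (renal toxicity, Grade 3): the same BGB324 instruction as Table 16. Pembrolizumab is stopped permanently.

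In all three tables the only permanent BGB324 stops are failure to resolve and Grade 4.

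The Grade 3 rows of Table 12 (Section 6.6.1) reduce to 100 mg at the first occurrence or "Discontinue permanently if dose has already been reduced". They also stop BGB324 permanently at a second "occurrence of same adverse event at G3". Table 13 does the same for QTc of Grade 3 or higher: a second occurrence is a permanent stop, and at the first the instruction is to restart at 100 mg or "discontinue treatment if dose reduction is not possible".

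**The concern.** The three toxicities singled out because both drugs may contribute are the only ones whose BGB324 table has no rule for recurrence. A site that follows Section 6.6.4 literally would restart a patient at 100 mg after a second Grade 3 rash, although the first rash had already led to that dose. For almost any other BGB324-related event the protocol would require the drug to be stopped. A site that also consults Table 12 would find the opposite instruction.

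This is a matter of patient safety and of consistent dosing between sites. Section 1.4.1 makes it more than theoretical. Gastrointestinal events of Grade 1 to 3 were the most common treatment-related events, seen in about half of patients in the two repeat-dose studies, and reversible creatinine increases were also reported. The same section says most gastrointestinal events responded to symptomatic treatment, and it gives no rate of recurrent Grade 3 events.

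**Working it through.** No formula applies, so the check sets the instructions side by side. These are all the Grade 3 rows that take BGB324 to 100 mg:

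| Source | First Grade 3 event | Second Grade 3 event | Dose already reduced |
|---|---|---|---|
| Table 12, general | Hold, then 100 mg | Permanent stop | Permanent stop |
| Table 13, QTc | Hold, then 100 mg | Permanent stop | Stop (no reduction possible) |
| Table 15, diarrhea (cycle 2 or later) | Hold up to 14 days, then 100 mg | Not addressed | Not addressed |
| Table 16, rash | Hold up to 14 days, then 100 mg | Not addressed | Not addressed |
| Table 17, renal | Hold up to 14 days, then 100 mg | Not addressed | Not addressed |

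Tables 12–13 contain both stops in 2 of 2 rows. Tables 15–17 contain the recurrence stop in 0 of 3 and the prior-reduction stop in 0 of 3.

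**Following one patient.** A patient on 200 mg has a Grade 3 rash that resolves within the hold and restarts at 100 mg. A second Grade 3 rash then occurs and also resolves within 14 days.

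- If Section 6.6.4 replaces Table 12, Table 16 restarts the patient at the same 100 mg.
- If Table 12 also applies, Table 16 says restart and Table 12 says stop permanently. The protocol does not say which prevails.

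The same fork arises at a first Grade 3 rash in a patient reduced earlier for another toxicity.

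**Does other text close the gap?** Section 6.6.1 allows only one reduction, and the notes to Table 12 say a dose below 100 mg is not possible. Restarting at 100 mg breaches neither. The recurrence note under Table 14 belongs to the pembrolizumab table. Section 3.3 lets the investigator stop treatment at any time, and the Table 12 notes allow discussion with the Medical Monitor, but both are discretionary.

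**How far it reaches.** Section 6.8 states: "Patients should not receive BGB324 during periods of systemic corticosteroid treatment". Section 6.11 repeats that patients on oral or intravenous steroids "must interrupt treatment with BGB324 throughout the duration of therapy". For events judged related to pembrolizumab, Section 6.11 calls for systemic steroids at Grade 3 for diarrhea/colitis and for renal events, with a taper of at least 4 weeks. That is 4 × 7 = 28 days, and 28 / 14 = 2, so the taper alone is at least twice the permitted hold. Those patients cannot restart within it. Section 6.11 has no rash entry, but Table 16's Grade 3 pembrolizumab cell refers to reducing corticosteroids, so steroid use is expected for some rashes too. What remains is mainly diarrhea or renal events attributed to BGB324, and rash not treated with systemic steroids.

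**The case against.** The best counter-argument is that Table 12 was never switched off. Section 6.6 says other toxicities can be managed under Sections 6.6.1–6.6.3, which is permissive wording. Section 6.6.1 and Table 12 cover BGB324-related toxicity without excluding the three events. Table 15 covers only diarrhea from cycle 2 onward, so if Table 12 were excluded, Grade 3 diarrhea in cycle 1 would have no BGB324 dose rule. Section 3.5 (compliance) and Section 5.3.9 (ECGs after an interruption) also treat Sections 6.6.1 and 6.6.2 as the general BGB324 rules. On this view, restarting at 100 mg is simply the one permitted step down from 200 mg.

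That reading is plausible, and it defeats the stronger inference that the protocol authorises unlimited rechallenge; that is one of two readings. It does not remove the problem. Section 6.6.4 never refers to Table 12, its restart instruction is not limited to first events, and if both tables apply, a second Grade 3 event carries contradictory orders.

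Three narrower points stand:

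- Table 12's stop depends on the dose having been reduced. A reader might infer that it covers anyone taking 100 mg, but it does not expressly cover a patient who started at dose level -1.
- Rash is not wholly outside the steroid restriction, as Table 16 shows.
- After Grade 3 renal toxicity a repeat event would occur on BGB324 alone, but it need not be a BGB324 effect: Section 6.6.3 notes that pembrolizumab events can appear months after the last dose.

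**Conclusion.** The point holds in limited form. For a second Grade 3 event, or a Grade 3 event after a reduction, the protocol gives either a restart at an unchanged 100 mg or two conflicting instructions. On neither reading is the stop that the sponsor wrote into Table 12 stated without contradiction for diarrhea, rash and renal toxicity.

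The conclusion is confined to BGB324 at Grade 3, to diarrhea with onset in cycle 2 or later for Table 15, and to events that resolve within 14 days without systemic steroids. It assumes the 14-day hold also binds patients who receive steroids; Section 6.8 allows a restart when steroids end and does not say how that fits with the limit.

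The documents do not support reading this as affecting every Grade 3 event of these types, and they give no basis for a patient count. Sample size, power and type I error are unaffected. It is worth correcting at the next amendment because a mandatory safety stop is left to inference.

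**What to change.** Add to Section 6.6.4: *The Grade 3 discontinuation rules of Table 12 also apply to diarrhea, rash and renal toxicity. BGB324 is permanently discontinued at a second Grade 3 occurrence of the same event, or at a Grade 3 event when the dose has already been reduced to 100 mg. This takes precedence over the restart at 100 mg in Tables 15–17.*

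For patients started at dose level -1, Table 12 is not explicit. State in both Table 12 and Section 6.6.4 that a Grade 3 event leads to discontinuation because no further reduction is possible, as Table 13 already does for QTc. This goes slightly beyond aligning the tables, so it should be made in both places to avoid creating a new difference.

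The cost is a few sentences in an amendment, with no extra patients, visits or procedures. The downside is that a few patients would stop BGB324 earlier than under a literal reading of Tables 15–17.

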#### 6.6.4.2 Dose modifications for rash (including dermatitis, pruritus) – [Table 16](#)

**Table 16: Pembrolizumab and BGB324 Dose Modification for Rash**

Rash – onset during any cycle	Pembrolizumab	BGB324
Grade 2	Pembrolizumab can continue as scheduled	BGB324 can continue as scheduled
Grade 3 or severe	Withhold for up to 12 weeks of last dose 
 
• If resolved to grade 0 or 1, restart pembrolizumab
 
• Permanently discontinue if not resolved to grade 0 or 1, or, there is an inability to reduce corticosteroid to <math>\leq 10</math> mg (prednisone or equivalent) per day
 
	Withhold for up to 14 days. 
 
• If resolved to grade 0, 1 or tolerable grade 2, restart at 100 mg qd
 
• Permanently discontinue if not resolved to grade 0, 1 or tolerable grade 2
 

Grade 4	Permanently discontinue	Permanently discontinue

#### 6.6.4.3 Dose modifications for renal toxicity (renal failure, serum creatinine elevation, nephritis) – [Table 17](#)

**Table 17: Pembrolizumab and BGB324 Dose Modification for Renal Toxicity**

Renal failure, serum creatinine elevation, nephritis – onset during any cycle	Pembrolizumab	BGB324
Grade 2	Withhold for up to 12 weeks of last dose 
 
• If resolved to grade 0 or 1, restart pembrolizumab
 
• Permanently discontinue if not resolved to grade 0 or 1, or, there is an inability to reduce corticosteroid to <math>\leq 10</math> mg (prednisone or equivalent) per day
 
	Withhold for up to 14 days 
 
• If resolved to grade 0 or 1, restart at 100 mg qd
 
• Permanently discontinue if not resolved to grade 0 or 1
 

Grade 3	Permanently discontinue	Withhold for up to 14 days 
 
• If resolved to grade 0, 1 or tolerable grade 2, restart at 100 mg qd
 
• Permanently discontinue if not resolved to grade 0, 1 or tolerable grade 2
 

Grade 4	Permanently discontinue	Permanently discontinue

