### 6.6.1 BGB324 dose modification for toxicity

If a patient experiences drug related toxicity that requires treatment with BGB324 to be interrupted, a delay of up to 14 days is permitted to allow for resolution of toxicity. In the absence of recovery, treatment with BGB324 should be discontinued. See [Table 12](#).

If treatment with BGB324 is interrupted, the relevant toxicity must have resolved to  $\leq$ Grade 1 or tolerable Grade 2 or baseline for treatment to recommence.

Only one dose reduction from 200 mg to 100 mg daily dose is possible.

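### Table 17 sets a stricter BGB324 restart condition after Grade 2 renal toxicity than after Grade 3, so the same tolerable Grade 2 state at day 14 means permanent stop in one row and restart in the other

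*Protocol*

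**What the plan says.** Section 6.6 of the protocol states that "Three toxicities have been identified as potentially overlapping with both BGB324 and pembrolizumab", names diarrhea, rash and renal toxicity, and sends their management to Section 6.6.4. All other toxicities fall under Sections 6.6.1 to 6.6.3. Renal failure, serum creatinine elevation and nephritis are therefore governed by Table 17.

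BGB324 column of Table 17:
- Grade 2: withhold for up to 14 days. "If resolved to grade 0 or 1, restart at 100 mg qd". Permanent discontinuation if Grade 0 or 1 is not reached.
- Grade 3: withhold for up to 14 days. "If resolved to grade 0, 1 or tolerable grade 2, restart at 100 mg qd". Permanent discontinuation only if none of these states is reached.
- Grade 4: permanent discontinuation.

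Pembrolizumab column: at Grade 2 it is withheld for up to 12 weeks from the last dose and may restart at Grade 0 or 1. At Grade 3 and Grade 4 it is permanently stopped.

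The general BGB324 rule in Section 6.6.1 asks for resolution to "Grade 1 or tolerable Grade 2 or baseline for treatment to recommence".

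**The concern.** A restart condition would normally be at least as strict after a worse event as after a milder one. In the BGB324 column of Table 17 the order is reversed, although hold length and restart dose are the same in both rows. An investigator who follows the table withdraws the investigational drug for good from a patient whose renal event never exceeded Grade 2. The same investigator re-doses a patient who reached Grade 3 and has come down to the identical state.

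The table also leaves the next step unclear. The patient restarted at tolerable Grade 2 is at the grade for which the Grade 2 row calls for a hold, and nothing says whether that row now applies. Sites could resolve this differently. At stake are consistent dosing and interpretable counts of permanent BGB324 discontinuation for renal events.

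**Working it through.** No plan figure needs reproducing. The check sets the dosing rules side by side.

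**Step 1. Table 17 as a decision table (BGB324, end of the 14-day hold).**

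| State at end of hold | Event peaked at Grade 2 | Event peaked at Grade 3 |
|---|---|---|
| Grade 0 or 1 | restart at 100 mg | restart at 100 mg |
| Tolerable Grade 2 | permanent stop | restart at 100 mg |
| Intolerable Grade 2 | permanent stop | permanent stop |
| Grade 3 | not applicable | permanent stop |

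The columns disagree in one line only, tolerable Grade 2, and there the milder peak has the irreversible outcome.

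**Step 2. The other BGB324 tables.**

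| Table | After Grade 2 | After Grade 3 | Stricter after Grade 2? |
|---|---|---|---|
| 12 (general toxicity) | "Interrupt treatment until toxicity returns to baseline, Grade 1 or tolerable Grade 2" | same condition | no |
| 13 (QTc) | Grade 1 or less "by 14 days from initial recording, restart BGB324 at a reduced dose of 100mg" | same condition | no |
| 15 (diarrhea) | one row for Grades 2-3: "If resolved to grade 0 or 1, restart BGB324 at 100 mg qd" | same row | no separate conditions |
| 16 (rash) | no hold | "Permanently discontinue if not resolved to grade 0, 1 or tolerable grade 2" | no Grade 2 restart condition |
| 17 (renal) | Grade 0 or 1 | Grade 0, 1 or tolerable Grade 2 | yes |

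Tables 15 and 16 do not offer two restart conditions to compare. The fair count is 1 of 3 (Tables 12, 13 and 17).

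**Step 3. Does another rule override the Grade 2 row?** Section 6.6.1 would accept tolerable Grade 2, but Section 6.6 routes renal toxicity to 6.6.4. No note under Table 17 explains or relaxes the difference.

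**Step 4. Safety run-in count (Section 8.2.1).** The count pools BGB324 dose reduction with permanent discontinuation of either drug; a significant rate is 4 or more of 6 patients, then 5 or more of 12.
- Grade 2 patient at tolerable Grade 2 on day 14: counts 1 as discontinued under the present rule, and would count 1 as reduced if restarted at 100 mg.
- Grade 3 patient: counts 1 in any case, because pembrolizumab is permanently stopped.

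The change in the count is 1 − 1 = 0 for each patient, so the thresholds are reached or missed exactly as before.

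**Step 5. Primary analysis.** Evaluability (Sections 3.5 and 8.4) needs one combination dose and measurable disease, so a later BGB324 stop removes nobody from the denominator. The power of 80.6% and one-sided error of 0.048 in Section 8.1 are computed for response rates of 0.35 and 0.20 and fixed stopping boundaries; no dosing rule enters.

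**Step 6. Systemic steroids.** Sections 6.8 and 6.11 interrupt BGB324 for the whole steroid course, and for renal events the taper starts at Grade 1 or less and lasts at least 4 weeks (28 days, against a 14-day hold). A steroid-treated patient still at Grade 2 on day 14 cannot restart that day under either row. Section 6.8 does allow restart once steroids are completed, however, and the protocol does not say how that permission interacts with the 14-day limit. The contrast is clearest in patients not on steroids, but the text does not confine it to them.

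**The case against.** The best defence is that the two rows describe different regimens. After a Grade 2 event pembrolizumab may return, also at Grade 0 or 1, so the strict BGB324 condition could be meant to protect a return to the combination. After a Grade 3 event pembrolizumab is gone, and the BGB324 condition for Grade 3 matches the general rule in Section 6.6.1. This is plausible, and it means the difference cannot be called a proven drafting error. But the protocol nowhere states it. Nor does it explain why, at day 14, with pembrolizumab withheld in one patient and stopped in the other, the same renal state should end BGB324 only after the milder event.

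A reader might infer that the Grade 2 patient is treated more harshly overall. The document does not support that. Pembrolizumab may still resume if the event resolves within 12 weeks of the last dose, and monotherapy is permitted (Sections 3.3 and 4.2). The Grade 3 patient keeps at most BGB324 100 mg. The inversion concerns the BGB324 column alone.

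A reader might also infer that the case is common, because Section 1.4.1 reports reversible creatinine increases with BGB324. That text says only that they were more frequent in patients with NSCLC. It gives no grade or duration for creatinine and no data in this disease. How often Grade 2 would persist to day 14 cannot be derived.

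**Conclusion.** The inversion is real and follows from the table's wording without any numerical assumption: one residual state, two opposite BGB324 decisions, the irreversible one after the milder peak. The accompanying conflict, restarting at a grade that calls for a hold, is also present.

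The consequence is minor and confined to individual BGB324 exposure and permanent discontinuations. That the number of affected patients is small is a judgment; the protocol gives no figure. It would overreach to read this as a threat to the run-in decision, to evaluability for objective response or to the error rates, since none of these changes. The conclusion rests on Table 17 governing renal events, as Section 6.6 directs, and on the rows being chosen by the peak grade of the event.

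**What to change.** Use one BGB324 restart condition in both rows. The preferred change is to give the Grade 3 row the wording of the Grade 2 row: "If resolved to grade 0 or 1, restart at 100 mg qd", with permanent discontinuation if Grade 0 or 1 is not reached within the hold. This removes both the inversion and the restart at a grade that requires a hold. It is an edit to one table cell.

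The cost is clinical. A few Grade 3 patients who settle at tolerable Grade 2 would lose BGB324 when pembrolizumab is already permanently stopped, and so would have no study treatment left. The row would also depart from the general rule in Section 6.6.1, as the QTc and diarrhea tables already do.

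The alternative is to relax the Grade 2 row to accept tolerable Grade 2 at day 14. That cures the inversion, but patients would restart while still at the grade that triggered the hold, so it is the weaker choice. A note giving a reason for the present difference would help readers, but would not by itself settle which row applies to a patient restarted at tolerable Grade 2.
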